On Days 1 through 29 or until discharge from inpatient hospitalization, whichever is earlier, need for RRT, 8-point ordinal scale of clinical status, vital signs, respiratory status measurement, adverse events (AEs), and concomitant medications will be documented. Following discharge from inpatient hospitalization, RRT status, 8-point ordinal scale of clinical status, AEs, concomitant medications, and mortality will also be collected during the Day 29 and Day 60 phone follow-up. Laboratory testing during hospitalization will be performed according to SOC practice with results for chemistry, hematology, and any SARS-CoV-2 testing being reported to the sponsor.

Even if not performed as SOC, SCr will be completed at screening, and on Days 1 through 29, or until discharge, whichever is earlier. In addition, even if not performed as SOC, chemistry, hematology, and coagulation will be completed at screening and on Days 1, 3, 5, 8, 12, 16, 20, 24, and 29 or until discharge, whichever is earlier.

CCI

CCI [REDACTED]

[REDACTED] CCI [REDACTED] CCI [REDACTED]

[REDACTED]

[REDACTED]

[REDACTED] CCI [REDACTED]

Test Product, Dose, and Mode of Administration:	Remdesivir for injection, 100 mg, for IV administration (lyophilized preparation)
--	---

Reference Therapy, Dose, and Mode of Administration:	Saline as placebo
---	-------------------

Criteria for Evaluation:

Safety:	The safety of RDV will be assessed during the study through the reporting of treatment-emergent AEs and serious adverse events (SAEs), as well as treatment-emergent clinical laboratory abnormalities.
---------	---

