6.4. Assessments (Days 2 Through 29)

The following evaluations are to be completed daily (unless otherwise noted in indicated sections and [Appendix 3](#)) from Day 2 through Day 29 or until discharge from inpatient hospitalization, whichever is earlier. If the participant is readmitted to the hospital prior to Day 29, evaluation for RRT, ordinal scale and AEs are to be completed daily through Day 29.

Participants must complete the following assessments before being administered investigational drug:

- Vital signs (heart rate, temperature, blood pressure)
- Documentation of respiratory status:
 - Respiratory rate
 - Oxygenation: SpO₂, room air, low-flow O₂, high-flow O₂, CPAP/BIPAP, mechanical ventilation, venovenous ECMO, venoarterial ECMO, and target FIO₂. The target FIO₂ value applies to all forms of O₂ nasal and mask delivery (nasal prongs, masks, CPAP/BIPAP) as well as mechanical ventilation

- IMV (yes/no; if yes, provide date when mechanical ventilation was started)
- Assessment of need for RRT
- Record the 8-point ordinal scale (see Section 6.9)
- Review AEs and document concomitant medications
- Laboratory evaluations: Chemistry, hematology, coagulation, and SCr (see Section 6.5)

█ [REDACTED]

█ [REDACTED]

- Collection of nasopharyngeal swab sample for SARS-CoV-2 RT-qPCR testing CCI [REDACTED]
[REDACTED] (see Section 6.8)

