6.10. Posttreatment Assessments

Upon discharge from inpatient hospitalization, the following assessments will be required at the Day 29 and Day 60 phone follow-up (see [Appendix 3](#)):

- Assessment of need for RRT
- Record the 8-point ordinal scale (see Section 6.9)
- Review AEs and document concomitant medications

- Mortality
- IMV (yes/no if yes, provide date when mechanical ventilation was started)
- Hospital readmission rate

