Appendix 3. Study Procedures Table

	Screening	Baseline/ Day 1	Day 2	Day 3	Day 4	Day 5	Day 6	Day 7	Day 8	Day 9, 10, 11	Day 12	Day 13	Day 14	Day 15	Day 16	Day 17, 18, 19	Day 20	Day 21	Day 22, 23	Day 24	Day 25, 26, 27, 28	Day 29*	Day 29 and Day 60 Phone Follow-up Visits (+ 5 days)
Written Informed Consent	X																						
Inclusion/Exclusion Criteria	X																						
Focused Medical History, including SCr values ^a	X																						
Documentation of SARS-CoV-2 Infection ^b	X																						
Complete Physical Examination	X																						
Height	X																						
Weight	X																						
Vital Signs ^c	X	X	X	X	X	X	X	X	X	X	X	X	X	X	X	X	X	X	X	X	X	X	X
Respiratory Status ^d	X	X	X	X	X	X	X	X	X	X	X	X	X	X	X	X	X	X	X	X	X	X	X
Invasive Mechanical Ventilation ^g	X	X	X	X	X	X	X	X	X	X	X	X	X	X	X	X	X	X	X	X	X	X	X
Pulmonary Radiographic Imaging ^e	X																						
8-Point Ordinal Scale ^f	X	X	X	X	X	X	X	X	X	X	X	X	X	X	X	X	X	X	X	X	X	X	X
Pregnancy Test ^h	X																						
Chemistry ^{h,r}	X	X		X		X			X		X				X		X			X		X	
Hematology ^{h,r}	X	X		X		X			X		X				X		X			X		X	

	Screening	Baseline/ Day 1	Day 2	Day 3	Day 4	Day 5	Day 6	Day 7	Day 8	Day 9, 10, 11	Day 12	Day 13	Day 14	Day 15	Day 16	Day 17, 18, 19	Day 20	Day 21	Day 22, 23	Day 24	Day 25, 26, 27, 28	Day 29*	Day 29 and Day 60 Phone Follow-up Visits (+ 5 days)	
Coagulation ^{1,f}	X	X		X		X			X		X				X		X			X		X		
Serum Creatinine ^{r,s}	X	X	X	X	X	X	X	X	X	X	X	X	X	X	X	X	X	X	X	X	X	X	X	
Urinalysis ^l	X																							
RRT Assessment ^k	X	X	X	X	X	X	X	X	X	X	X	X	X	X	X	X	X	X	X	X	X	X	X	X
Virologic Testing ^l		X		X		X		X					X					X				X		

[figure not shown]
CCI

CCI

CCI

Investigational Drug Dosing		X	X	X	X	X																		
Adverse Events	X	X	X	X	X	X	X	X	X	X	X	X	X	X	X	X	X	X	X	X	X	X	X	X
Concomitant Medications	X	X	X	X	X	X	X	X	X	X	X	X	X	X	X	X	X	X	X	X	X	X	X	X
Mortality																							X	
Hospital Readmission Rate																							X	

* All assessments to be completed through Day 29, or until discharge, whichever is earlier. If participant is discharged prior to Day 29, a phone follow-up is to be completed at Day 29 and Day 60.

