6.2.1. Analysis of Secondary Efficacy Endpoints

The key α -controlled secondary endpoint of all-cause mortality through Day 29 will be analyzed in a similar manner to the primary endpoint.

Initiation of IMV through Day 29 and time to recovery through Day 29 will also be analyzed in a similar manner to the primary endpoint except that a competing risk analysis approach will be used with death as the competing risk.

For analysis on time to recovery through Day 29, two sets of analyses will be conducted:

(1) Time to recovery through Day 29, in which the first recovery without further worsening in the ordinal scale score (ie, a score of > 4) by Day 29 will be considered an event; (2) Time to recovery through Day 29, in which the first recovery (regardless of further worsening or not) will be considered an event.

The clinical status assessed by the 8-point ordinal scale at Day 15 and Day 29 will be analyzed using a proportional odds model including treatment as the independent variable. Two models will be explored; one with baseline score as a continuous covariate and one without baseline score as a covariate. The odds ratio and 95% CI will be provided. The percentage of participants in each category will be summarized by treatment group. The assumption of odds proportionality will be assessed using a score test and reported. Clinical status by study day and change from baseline up to Day 29 will also be summarized by treatment group.

For participants without ESKD at baseline, the number of RRT-free days will be calculated between date of first dose and Day 29. The number of RRT-free days will be calculated as the number of full days from Day 1 to Day 29 that the participant was alive and did not receive RRT. The number of RRT-free days will be summarized by treatment group, and compared between treatment groups using Wilcoxon rank sum test.

The proportion of participants with recovery through Day 29 will be summarized by treatment group, and compared between treatment groups using the CMH test stratified by randomization strata. Similar for time to recovery analysis, two sets of analyses will be conducted: (1) The proportion of participants with recovery through Day 29, in which recoveries without further worsening by Day 29 is considered; (2) The proportion of participants with recovery through Day 29, in which recoveries regardless of worsening status by Day 29 is considered.

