7.2. Laboratory Evaluations

Laboratory data collected during the study will be analyzed and summarized using both quantitative and qualitative methods. Summaries of laboratory data will be provided for the Safety Analysis Set and will include data collected up to the last dose of study drug plus 30 days. The analysis will be based on values reported in conventional units. When values are below or above the LOQ, they will be listed as such, and the closest imputed value will be used for the purpose of calculating summary statistics as specified in Section 3.7.

Because RRT may significantly impact certain lab values such as SCr and BUN, a sensitivity analysis will be conducted, in which records and/or participants may be excluded from analysis as follows:

- SCr and BUN will only be analyzed for participants who are not on RRT at baseline. If RRT is used during the study, any records from RRT start to end + 3 days will be excluded from analysis.

RRT started within 3 days before first dose is considered RRT at baseline.

Anticoagulation medications can impact coagulation lab parameters, such as aPTT, PT, and INR. Sensitivity analysis will be conducted for coagulation lab parameters. Any coagulation lab records under the influence of these medications will be excluded from analysis. For anticoagulation medications in the Warfarin class, coagulation lab records with a date in between the start and 5 + the stop date of the medication will be excluded; for other anticoagulation medications, records with a date in between the start and 1 + the stop date of the medication will be excluded.

A by-participant listing for laboratory test results will be provided by participant ID number and visit in chronological order for hematology, coagulation, serum chemistry, CCI [REDACTED] Values falling outside of the relevant reference range and/or having a severity grade of 1 or higher on the DAIDS Grading Scale (see Section 7.2.2) will be flagged in the data listings, as appropriate.

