- If the end date is incomplete but the month and year (or year alone) of the end date is before the month and year (or year alone) of the first dosing date of study drug, the event will not be included.

A variable for each of the risk factors will be added to raw Medical History and Adverse Events datasets. A medical history or an AE record will be flagged for a risk factor if its MedDRA PT is included in the prespecified PT list for the corresponding disease of interest, which includes all PTs from the narrow or broad search of the following SMQs under MedDRA 25.0 provided by

Gilead GLPS and reviewed by Gilead medical monitors.

Disease of Interest	SMQ or MedDRA HLT Source
Chronic lung disease	HLT of bronchospasm and obstruction
Hypertension	Hypertension (SMQ)
Cardiovascular or cerebrovascular disease	Ischaemic central nervous system vascular conditions (SMQ); Myocardial infarction (SMQ); Other ischaemic heart disease (SMQ)
Diabetes mellitus	Hyperglycaemia/new onset diabetes Mellitus (SMQ)
Immunocompromised state	HLGT for “Immunodeficiency syndromes”
Chronic liver disease	search name “Chronic liver disease excluding transient_acute events and nonspecific signs_symptoms”
Current cancer	Malignancies (SMQ)

10) Details on SCr and BUN record exclusion for sensitivity analysis

SCr and BUN will only be analyzed for participants who are not on RRT at baseline.

RRT at baseline:

RRT started within 3 days of first dose is considered RRT at baseline. An RRT record with an end date prior to the first dose date - 3 days (or 72 hours if time available) or a start date/time after the first dose date/time will not be considered a baseline RRT record; otherwise, the record will be considered baseline.

SCr/BUN record exclusion (for participants who are not on RRT at baseline):

Any SCr/BUN records from an RRT start to end + 3 days will be excluded from analysis.

If both date and time are collected for RRT and labs, only date will be used, with 1 exception below:

If an SCr/BUN record is collected on the first dose date and prior to first dose time, and the participant's first RRT starts on the first dose date but after first dose time, then this lab record will not be excluded.

RRT date:

A missing end date of a hemodialysis record will be imputed using the hemodialysis start date.

If an end date is missing for a CVVH record:

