- If this record is followed by another RRT (CVVH or hemodialysis) record, then the end date of this CVVH record will be imputed as the start date of the subsequent RRT record;
- If this record is the last available or the only RRT record for a participant:
 - If the participant died after the start of this CVVH record, then the end date of this CVVH record will be imputed as the death date;
 - Otherwise, the end date of this CVVH record will not be imputed, and all the SCr and BUN records after the start date of this CVVH record will be excluded from analysis.

11) Details on coagulation lab record exclusion for sensitivity analysis

Any coagulation lab records under the influence of anticoagulation medications will be excluded from analysis. For coagulation lab record exclusion, the start/end date of anticoagulation medications will be used. An anticoagulation medication may be taken chronically prior to and/or during the study.

Anticoagulation medication date:

If a medication end date is missing, the medication will be considered as “ongoing”, and all coagulation lab records after the medication start date will be excluded from analysis.

If a medication start date is missing, all coagulation lab records will be considered after the medication start date.

For a partial medication end date:

- If only date is missing, then the date will be imputed as the last date of the month;

- If both month and date is missing, then the month and date will be imputed as December 31st of the year.

For a partial medication start date:

- If only date is missing, then the date will be imputed as the first date of the month;
- If both month and date is missing, then the month and date will be imputed as January 1st of the year.

12) Treatment difference in percentages not adjusted by stratum

The percentage difference between two treatment groups and its 95% CIs are calculated based on the unconditional exact method using 2 inverted 1-sided tests in SAS v9.3 or above.

The following SAS code will be used to compute cell counts and p-values.

```
data example;
input grp trt $ outcome $ count ;

datalines;
1 Treat-A 2-Fail x
1 Treat-A 1-Succ xxx
1 Treat-B 2-Fail x
1 Treat-B 1-Succ xxx
run;

proc freq data = example;
table trt*outcome /riskdiff(CL=(exact)) alpha=0.05;
weight count; exact RISKDIFF(METHOD=SCORE);
output out=ciexact(keep=_RDIF1_ XL_RDIF1 XU_RDIF1 _RSK11_ _RSK21) riskdiff;
run;

data final(keep=A1 B1 Estimate LowerCL UpperCL ocharc1);
set ciexact;

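### RRT-free days are scored by receipt of RRT on each day, so the count may depend on dialysis modality, and no readable rule scores the days from discharge to Day 29

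*SAP*

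**What the plan says.** **Scoring.** SAP 6.2 restricts the endpoint to participants without ESKD at baseline. SAP 6.2.1 counts "the number of full days from Day 1 to Day 29 that the participant was alive and did not receive RRT" and compares arms with a Wilcoxon rank sum test. It defines neither an RRT course nor the handling of days between sessions.

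**Records.** The only readable handling of RRT dates is SAP Appendix 2 item 10, written for the creatinine and BUN sensitivity analysis. It says "A missing end date of a hemodialysis record will be imputed using the hemodialysis start date". A CVVH record without an end date runs to the next RRT record or to death. Failing both, "the end date of this CVVH record will not be imputed" and the record stays open.

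**Collection.** The daily item in Protocol 6.4 is "Assessment of need for RRT". It runs to Day 29 or discharge, whichever is earlier, and resumes on readmission. For the period after discharge:

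- The Protocol synopsis says "RRT status, 8-point ordinal scale of clinical status, AEs, concomitant medications, and mortality will also be collected during the Day 29 and Day 60" calls.
- Protocol 6.10 says "Upon discharge from inpatient hospitalization, the following assessments will be required at the Day 29 and Day 60 phone follow-up", and its list includes need for RRT. That list asks for a start date for IMV but for no RRT dates.
- The note to the Protocol Appendix 3 table says "If participant is discharged prior to Day 29, a phone follow-up is to be completed at Day 29 and Day 60". Footnote k on the RRT row, however, names only the Day 60 call. SAP Appendix 1 repeats that footnote.

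**Missing days.** SAP 3.6.1 imputes nothing unless a method is given. The discharge and carry-forward rules in SAP 6.2.1 apply to the ordinal scale only.

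**The concern.** There are two separate problems.

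1. A person who depends on intermittent hemodialysis is not dialyzed every day. If each session is its own record, the days between sessions meet the literal definition of RRT-free. A person equally dependent on continuous RRT gets no such days. The score then mixes which modality was used with whether the participant came off RRT, and only the second is of interest.

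2. The scoring window runs to Day 29, but scheduled daily assessment ends at discharge. If outpatient sessions are not entered, the days after discharge can be credited as free to someone still on dialysis. This is foreseeable: Protocol 1.1 notes that many surviving patients with pre-existing CKD need dialysis when they leave hospital.

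At stake is the meaning of the reported number of days. Protocol 4.3 excludes people on RRT for AKI, and the endpoint excludes ESKD, so only participants who start RRT after entry are affected.

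**Working it through.** The documents give no figure for this endpoint, so there is none to reproduce. The check applies the literal SAP count to example participants who survive to Day 29.

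**Inputs.** From SAP 6.2.1: a 29-day window, one point for each day without RRT. Assumed, not in the documents: three hemodialysis sessions a week at intervals of 2, 2 and 3 days, first session on Day 3. The three possible orders of these intervals give three phases.

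**Formula.** Score = 29 − (days on which RRT was received).

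**Step 1: RRT on Days 3 to 29, never weaned.**

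- Sessions with intervals 2-2-3: Days 3, 5, 7, 10, 12, 14, 17, 19, 21, 24, 26, 28.
- Intervals 2-3-2: Days 3, 5, 8, 10, 12, 15, 17, 19, 22, 24, 26, 29.
- Intervals 3-2-2: Days 3, 6, 8, 10, 13, 15, 17, 20, 22, 24, 27, 29.
- Each phase has 12 sessions: 29 − 12 = **17**.
- Continuous RRT: 29 − 27 = **2**.

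**Step 2: RRT stopped after Day 14.**

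- Continuous: 29 − 12 = **17**, a tie with never-weaned hemodialysis.
- Hemodialysis: 5 or 6 sessions, so 29 − 6 = 23 or 29 − 5 = 24.
- Credit for stopping (Step 2 minus Step 1): 6 to 7 days on hemodialysis, 17 − 2 = 15 on continuous RRT.

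**Step 3: range over session frequency.** For a participant dependent on all of Days 1 to 29:

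| Sessions per week (assumed) | Literal score |
|---|---|
| 2 | 20–21 |
| 3 | 16–17 |
| 4 | 12–13 |
| Daily or continuous | 0 |

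**Step 4: discharge.** Hemodialysis from Day 3, discharged on Day 12 still dialyzed.

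- All outpatient sessions entered: 29 − 12 = 17.
- None entered: 4 or 5 sessions are recorded by Day 12, so 29 − 5 = 24 or 29 − 4 = 25.
- A second assumed case (three a week from Day 6, discharged on Day 15) gives 18–19 with every session known and 24–25 with none after discharge.

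**Step 5: a course count.** Count every day from the first to the last session as an RRT day.

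- Never weaned, on RRT at Day 29: 29 − 27 = 2, the same as continuous RRT.
- Hemodialysis stopped after Day 14: last session on Day 14, 12 or 13, so 17, 19 or 18. Credit for stopping becomes 15 to 17 days, against 15 on continuous RRT.
- Step 4 participant, on RRT at Day 29: 2.
- Step 4 participant, off RRT with no stop date: last recorded session on Day 12 or 10, so 29 − 10 = 19 or 29 − 8 = 21. The latest possible stop, Day 28, gives 29 − 26 = 3.

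**The case against.** The strongest reply is that SAP 6.2.1 is explicit and matches the endpoint's name: it counts days without RRT and nowhere claims to measure dependence. That stands. The definition is a choice, not an error, and the literal count should still be reported. It does not make the count easy to read when hemodialysis and continuous RRT are mixed.

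Several stronger readings are tempting, and the documents do not support them.

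- **That session-level recording is a fact.** Item 10 treats a hemodialysis record as same-day and CVVH as an interval, which points that way. But it is a missing-date rule for laboratory data, the case report form is not shown, and the daily protocol item asks about need. If records cover whole courses, the modality problem does not arise.
- **That the SAP contradicts itself over creatinine and BUN.** SAP 7.2 says "If RRT is used during the study, any records from RRT start to end + 3 days will be excluded from analysis". This window removes laboratory values that RRT may distort. A day can be unsuitable for reading creatinine and still be a day without RRT.
- **That RRT after discharge is not captured.** Status is asked at the Day 29 call. RRT records carry dates, SAP 7.5 lists RRT during the study without limiting it to inpatients, and daily assessment resumes on readmission. What is missing from the readable text is the step from that status to daily scores. Redacted text may contain it.
- **That the Wilcoxon test is materially weakened.** In a simulation with 298 and 149 participants (80% of half of 1116, split 2:1) and assumed rates, the literal count cost at most 0.8 percentage points of power with 10% starting RRT, and at most 0.7 with no deaths. Larger losses needed 25% starting RRT, 25% deaths and weaning of 60% against 20%. Even there, power was below 15% under either count.

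**Conclusion.** The concern holds in limited form. The modality effect depends on session-level recording, which is inferred. Given that, and three sessions a week, never-weaned hemodialysis from Day 3 scores 15 days more than equally prolonged continuous RRT (17 − 2) and ties with continuous RRT stopped after Day 14. The discharge gap does not depend on the recording level: in the example it adds 7 to 8 days (24 or 25 − 17) if no outpatient session is entered.

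Importance is low. SAP 3.5 gives this endpoint no multiplicity control. The primary and key secondary tests and the type I error are unaffected, and power hardly changes. The consequence is a reported day count that is hard to interpret. It is still worth correcting, because this is the plan's renal efficacy endpoint in a kidney population and the data needed are largely collected already.

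**What to change.** Before unblinding:

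1. Report RRT-free days with every day from the first to the last session of a course counted as an RRT day, joining sessions no more than a prespecified gap apart, alongside the literal SAP count. The gap should tolerate a delayed session: if one 3-day interval stretches to 4 days, a 3-day gap splits the course and scores 5, while a 4- or 5-day gap scores 2. If records are already course-level, state that instead.
2. Let an observed Day 29 status decide whether a course is open. On RRT: run the course through Day 29. Off RRT: end it at the recorded stop date or, without one, at the last recorded session. That gives the single score for the Wilcoxon test, with the latest possible stop as a sensitivity bound (in the example 19 to 21, bound 3). Use the gap rule at Day 29 only when that status is missing, so that it never overrides an observed status.
3. Align footnote k in Protocol Appendix 3, and its copy in SAP Appendix 1, with the synopsis, Protocol 6.10 and the table, which all include the Day 29 call.

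The cost is SAP wording and modest programming. No new data collection is needed, since RRT status is already asked at the Day 29 call. The downsides are lower day counts in both arms and a gap length that is a judgment to fix in advance.

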A dosing duration of up to 5 days will be evaluated in this study. The 5 days dosing duration is the recommended IV RDV duration for treatment of COVID-19 requiring hospitalization and not requiring invasive mechanical ventilation (IMV) and/or extracorporeal membrane oxygenation (ECMO) {[VEKLURY 2020](#)}. Moreover, patients with COVID-19 who do not require mechanical ventilation, 5 days of RDV showed similar efficacy to a 10-day regimen. Similarly, 5 days treatment of RDV in participants with moderate COVID-19 was associated with a significant improvement in clinical status compared with standard of care (SOC) and approximately a third of participants were discharged prior to completion of 5 days RDV therapy.

In order to fully characterize the relationship between kidney function and RDV disposition, an additional Phase 1 study in non-COVID-19 participants with chronic renal impairment (mild, moderate, severe chronic impairment, and end-stage renal disease) is ongoing (GS-US-540-9015). PK and safety data from both studies will be used to inform the recommendations for the use of RDV in COVID-19 patients with varying degrees of renal impairment.

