6.9. Ordinal Scale

The ordinal scale is an assessment of the clinical status of a given study day. Each day, the worst (ie, highest ordinal) score from the previous day will be recorded (ie, on Day 3, the highest ordinal score from Day 2 is obtained and recorded for Day 2). The ordinal scale needs to be completed twice on Day 1: prior to randomization (for baseline predose score) and the worst score on Day 1.

The scale is as follows:

- 8) Death
- 7) Hospitalized, on IMV or ECMO
- 6) Hospitalized, on noninvasive ventilation or high-flow oxygen devices
- 5) Hospitalized, supplemental oxygen
- 4) Hospitalized, not requiring supplemental oxygen – requiring ongoing medical care for COVID-19–specific medical care (other than per-protocol RDV administration)
- 3) Hospitalized, not requiring supplemental oxygen – no longer requires ongoing medical care (other than per-protocol RDV/saline as placebo administration)
- 2) Not hospitalized, limitation on activities and/or requiring home oxygen
- 1) Not hospitalized, no limitations on activities

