3.8.2. Analysis Visit Windows

Participant visits might not occur on protocol-specified days. Therefore, for the purpose of analysis, observations will be assigned to analysis windows.

The analysis windows for chemistry (except for SCr), hematology and coagulation laboratory tests are provided in Table 3-1. CCI

Table 3-1. Analysis Visit Windows for Chemistry (Except for SCr), Hematology, and Coagulation Laboratory Tests

Nominal Visit	Nominal Study Day	Visit Window Study Day	
		Lower Limit	Upper Limit
Baseline	1	(none)	1 (Pre Dose)
Day 3	3	1 (Post Dose)	3
Day 5	5	4	6
Day 8	8	7	10
Day 12	12	11	14
Day 16	16	15	18
Day 20	20	19	22
Day 24	24	23	26
Day 29	29	27	44

The 8-point ordinal scale will be collected daily from Day 1 through Day 29 or discharge, whichever is earlier, as well as at the Day 29 and Day 60 phone follow-up. The analysis visit window will coincide with each study day up to Day 44 with 1 exception: a Day 1 postdose record will be mapped to Analysis Day 2 visit (the 8-point ordinal scale will be collected twice on Day 1: predose and the worst score on Day 1 post-dose). If any additional records are collected after Day 44, the analysis window is provided in [Table 3-3](#).

Table 3-3. Analysis Visit Window for 8-Point Ordinal Scale Collected after Day 44

Nominal Visit	Nominal Study Day	Visit Window Study Day	
		Lower Limit	Upper Limit
Day 60	60	45	(none)

Vital signs, and SCr will be collected daily from Day 1 through Day 29 or discharge, whichever is earlier, per protocol; therefore, the analysis visit window will coincide with each study day up to Day 29 with 1 exception: a Day 1 postdose record will be mapped to Analysis Day 2 visit.

3.8.3. Selection of Data in the Event of Multiple Records in an Analysis Visit Window

Depending on the statistical analysis method, single values may be required for each analysis window. For example, change from baseline by visit usually requires a single value, whereas a time-to-event analysis would use all data regardless of analysis window.

If multiple valid, nonmissing measurements exist in an analysis window, records will be chosen based on the following rules if a single value is needed:

- For baseline, the last nonmissing value on or prior to the first dosing date (and time, if available) of study drug will be selected, unless specified differently. If there are multiple records with the same time or no time recorded on the same day, the baseline value will be selected as follows:

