The key α -controlled secondary endpoint of all-cause mortality through Day 29 will also be analyzed for each of the subgroups defined in Section 3.4. Other secondary endpoints may also be analyzed for each of the stratification factor subgroups.

For time to event analysis of secondary endpoints, participants with missing outcomes due to premature discontinuation of the study on or prior to Day 29 will be censored at the date of last known status for that endpoint.

Clinical status assessed by the 8-point ordinal scale will be derived by combining the available death, hospital discharge alive and ordinal scale assessment reported by the site, where death supersedes discharge alive and discharge alive supersedes the ordinal scale score reported by the site.

Sites were instructed to report the worst ordinal scale category for each day. Therefore, the ordinal scale result on the day the participant was discharged alive does not necessarily reflect Not hospitalized. The definition of clinical status based on the 8-point ordinal scale is defined as follows:

- If a participant dies on or prior to Day 29, clinical status on the day of death and all subsequent days through Day 29 will be set as 8 (death)
- If a participant is discharged alive on or prior to Day 29, clinical status on the day of discharge alive will be set to 2 (not hospitalized, limitation on activities and/or requiring home oxygen), which is the worst score for a non-hospitalized participant
- If a participant is discharged alive and subsequently re-admitted on or prior to Day 29, and the 8-point ordinal score is not reported on the day of re-admission, the clinical status on the day of the re-admission will be imputed to 7 (hospitalized, on IMV or ECMO), which is the worst score for a hospitalized participant
- For other missing ordinal scores from Day 2 through Day 29, the clinical status will be imputed using the previous day's score (either reported score or imputed score as applicable)

The FAS will be the primary analysis set for the secondary efficacy endpoints.

CCI

[REDACTED]

- [REDACTED]
- [REDACTED]
- [REDACTED]
- [REDACTED]
- [REDACTED]
- [REDACTED]
- [REDACTED]
- [REDACTED]
- [REDACTED]
- [REDACTED]
- [REDACTED]

CCI

CCI

CCI

CCI

CCI

CCI [Redacted]

CCI [Redacted]

[Redacted]

[Redacted]

[Redacted]

[Redacted]

[Redacted]

[Redacted]

[Redacted]

[Redacted]

[Redacted]

[Redacted]

[Redacted]

CCI

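### Under scheduled collection, everyone alive, discharged and not readmitted by Day 15 is carried at category 2, so the category 1 and 2 percentages at Day 15 are not measurements, and the split at Day 29 partly reflects the date of the call

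*SAP*

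**What the plan says.** Protocol Section 6.9 separates two levels outside hospital. Category 1 is "Not hospitalized, no limitations on activities"; category 2 covers limited activity, home oxygen or both.

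Protocol Section 6.4 has the scale scored daily until discharge. Once a participant has left hospital, Section 6.10 says that "the following assessments will be required at the Day 29 and Day 60 phone follow-up". SAP Section 3.8.2 agrees: the scale is collected "daily from Day 1 through Day 29 or discharge, whichever is earlier, as well as at the Day 29 and Day 60 phone follow-up". No scheduled contact falls between discharge and the Day 29 call.

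SAP Section 6.2.1 derives the analysed score. Death overrides discharge, and discharge overrides the site's score. The rule for discharge is that "clinical status on the day of discharge alive will be set to 2 (not hospitalized, limitation on activities and/or requiring home oxygen", which the SAP describes as the worst score for someone out of hospital. An unscored day of readmission becomes 7. For other missing days, "the clinical status will be imputed using the previous" day's score, whether that was reported or itself imputed.

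The same section fits a proportional odds model at Day 15 and Day 29 and adds that "The percentage of participants in each category will be summarized by treatment group". It also plans clinical status by study day and change from baseline up to Day 29.

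**The concern.** The discharge rule fixes one day. Combined with the carry-forward rule and the collection schedule, it fixes every day up to the call. The Day 15 table would then say that all participants out of hospital have limited activity or need home oxygen, which nobody assessed. The SAP does not say that category 1 is empty at Day 15.

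Two further effects follow. Category 1 first becomes available when the call is made, so the by-day and change-from-baseline summaries can show an improvement at Day 29 that the schedule produced. And because the call may be made after Day 29, the Day 29 split between categories 1 and 2 depends partly on when the site telephoned.

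**Working it through.** The documents state no figure for this endpoint, so there is none to reproduce. The check applies the SAP rules to the protocol schedule.

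**Inputs**
- Scale: Protocol 6.9.
- Collection: Protocol 6.4, 6.10 and the Appendix 3 footnote on discharge before Day 29; SAP 3.8.2.
- Derivation: SAP 6.2.1.
- Call window: +5 days (Protocol Appendix 3, last column), so Days 29 to 34.
- Analysis window for the scale: one per study day up to Day 44 (SAP 3.8.2), so a call on Days 30 to 34 does not map to Day 29.

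**Step 1: the carried score.** Let S(t) be the derived status and D the discharge day, with D at or before Day 15, and no readmission or death. Then S(D) = 2. For t = D+1 to 28 there is no scheduled score, so S(t) = S(t−1) = 2. Hence S(15) = 2.

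**Step 2: example paths, with every call scored 1.**

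| Path | Day 15 | Day 28 | Day 29 |
|---|---|---|---|
| Discharged Day 6, call Day 29 | 2 | 2 | 1 |
| Discharged Day 15, call Day 29 | 2 | 2 | 1 |
| Discharged Day 6, call Day 31 | 2 | 2 | 2 |
| Discharged Day 6, readmitted Day 12, readmission unscored | 7 | 7 | 7 |
| Discharged Day 6, died Day 12 | 8 | 8 | 8 |

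Enumerating discharge on Days 2 to 29, optional readmission and second discharge, and calls on Days 29 to 34 gives 19,824 paths. None has a 1 at Day 15. The enumeration assumes that scoring stops again at a second discharge. Protocol 6.4 can be read as continuing daily scores to Day 29 after any readmission, so the point is limited to participants not readmitted.

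**Step 3: Day 29.** If the call is on Day 29, S(29) is the call score. If it is on Days 30 to 34, S(29) = S(28) = 2. Two participants in the same condition, both without limitations, are scored 1 and 2 because of the call date.

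**Step 4: size.** Let d be the share of participants alive and out of hospital, and f the share of those who are truly category 1. The share mislabelled is d × f, and the mean score is d × f × 1 point too high. The documents give neither d nor f. Assumed values:

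| d | f = 10% | f = 50% | f = 75% |
|---|---|---|---|
| 40% | 4% | 20% | 30% |
| 70% | 7% | 35% | 52.5% |

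The artificial fall in the mean score at Day 29 is d × f × q, with d and f now taken at Day 29 and q the share of these participants whose call is on Day 29 itself. The documents do not give q either. If q = 0 there is no step; if q = 1 it is the full d × f.

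**Step 5: the Day 15 model.** The model code in SAP Appendix 2, item 22, fits the levels present in the data. An empty category 1 adds no cut-point, so calling the scale 8-level or 7-level gives the same odds ratio.

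**The case against.** The strongest reply is that the rule is stated openly, was chosen as the conservative value for someone out of hospital, and applies equally to both arms. The endpoint is outside the multiplicity control. Recovery is unaffected, because categories 1, 2 and 3 all count. All of this stands. It explains the score on the day of discharge, when sites record the day's worst status. It does not justify presenting a carried value as an observed category for up to about four weeks.

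It is also fair that the size rests on assumptions. The one figure on discharge, in Protocol Section 1.4, is that "approximately a third of participants were discharged prior to completion of 5 days RDV therapy". It comes from moderate COVID-19, not from patients with severely reduced kidney function, and says nothing about the split between categories 1 and 2.

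Several stronger readings are tempting, and the documents do not support them:
- *All discharged participants are affected.* Those readmitted by Day 15 receive hospital scores, or 7 on an unscored day of readmission, and those who died receive 8.
- *Category 1 is impossible at Day 15.* It is unreachable by scheduled collection. An unscheduled site score would not be missing and could be used, although neither document provides for one.
- *The Day 15 treatment comparison is distorted, or one arm favoured.* The odds ratio is the same whether or not the empty level is merged, and nothing in the rule distinguishes the arms.
- *The point is a loss of statistical information.* The documents give no distribution from which to size such a loss, and recoding would not recover it, so it is no argument for the change.
- *Everyone discharged steps down at Day 29.* The step arises only for calls made on Day 29.

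**Conclusion.** The concern holds as a fault in what the tables report. Under scheduled collection, the Day 15 percentages in categories 1 and 2 are produced by the scoring rule. The by-day and change-from-baseline summaries inherit the same error and can step at Day 29. The share mislabelled is d × f: 4% to 52.5% over the assumed ranges, and above zero whenever some discharged participants have no limitations.

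The one place where a model estimate could change is Day 29, where observed 1s from calls on the day are mixed with carried 2s from later calls. The documents give no reason to expect call timing to differ by arm, so neither a direction nor a size can be claimed.

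**What to change.** Amend SAP Sections 6.2.1 and 3.8.2 as follows.

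1. Before the Day 29 call, report categories 1 and 2 as one level, *not hospitalized*, including any unscheduled scores after discharge. Describe Day 15 as a 7-level scale.
2. In the by-day and change-from-baseline summaries, use the collapsed scale on all days, including Day 29.
3. For the Day 29 proportional odds model, either assign a Day 29 call made within its +5-day window to Day 29, with death and readmission by Day 29 still taking precedence, or collapse categories 1 and 2 there too. Report the 1-versus-2 split only from actual call scores.

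The cost is SAP wording and a recode of data already planned. The downside is that Day 15 becomes a 7-level endpoint. A scored Day 15 contact would have been needed to observe the split, but SAP Section 2.4 records that enrollment has stopped, so the recode is the practical course.
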